10.4 Data Analysis

Descriptive statistics, including mean, median, standard deviations, and ranges for all continuous measures, will be tabulated and reported. Percentages and frequencies for all categorical measures will also be presented. Time-to-event endpoints will be reported using Kaplan-Meier estimates, with 95% CIs for median time to event.

10.4.1 Demographics and Baseline Characteristics

Demographic and baseline disease characteristics will be summarized using descriptive statistics. Data to be tabulated will include demographic features such as age, sex, and race, as well as disease-specific characteristics.

The number and percentages of patients enrolled, treated, completed the treatment/study and withdrawn from treatment/study for any reason will be presented.

10.4.2 Efficacy Analysis

All efficacy analyses will be performed using the Efficacy Analysis Set.

The ORR is defined as the proportion of patients achieving a response of CR or CRi at the time of the recovery assessment. For ORR, point estimates and the associated 95% CIs (based on the Clopper-Pearson method) will be calculated.

For DOR, the estimate of the median based on Kaplan-Meier analyses will be reported. For EFS and OS, the estimated rates at 6, 12, and 24 months based on Kaplan-Meier analyses will be reported.

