5. STUDY DESIGN

This is a multi-center, non-randomized, open-label, two-part prospective Phase II clinical trial in patients with relapsed or refractory FLT3-ITD mutation-positive AML. The study is designed to assess the safety and tolerability as well as the efficacy of administering CPX-351 (cytarabine:daunorubicin liposome complex) with quizartinib, a second-generation FLT3 inhibitor. The plan for administration is divided into three phases: induction, consolidation, and maintenance. Approximately 34 patients are planned to be screened and enrolled. Patient participation is expected to be 4 years.

A total of 10 patients will be enrolled in the safety lead-in. The safety lead-in portion of the study is designated as Part 1. If >3 patients experience delayed neutrophil count recovery >56 days from the first day on the study regimen, or delayed thrombocytopenia recovery >56 days from the first day on the study regimen, or if >3 patients develop a non-hematologic toxicity, defined as a Grade 4 non-hematologic adverse event determined to be probably related to the combined treatment, or a Grade 4 neutropenia, then the study will be terminated.

Assuming safety parameters are met, the first 10 patients will be followed for response in the Part 2 of the study. An additional 24 patients will be enrolled in Part 2 of the study (induction, consolidation and maintenance). All patients will be assessed for response.

Patients who fail to respond to therapy will be followed until a new therapy is instituted. . Patients who experience an AE that results in the discontinuation of study treatment will be

[figure not shown]
CONFIDENTIAL

STUDY DRUG: QUIZARTINIB
PROTOCOL DATE: 10 AUGUST 2020

DEVELOPMENT INNOVATIONS STUDY NUMBER: AML 48
VERSION 4.0

followed until resolution/stabilization for AEs attributed to the medication. Outcomes for all patients will be assessed for 24 months from the date of last treatment.

Figure 1 Study Schema

*All treatment phases follow a 28-day cycle. Induction and re-induction consist of: CPX-351 (liposomal daunorubicin 44 mg/m² IV and cytarabine 100 mg/m² IV) + quizartinib 30 mg PO QD. The maintenance phase: begin quizartinib 30 mg PO QD on Days 1-14. If there are no toxicities and QTcF is maintained ≤ 450 msec, increase dose to 60 mg QD on Day 15.

[†]For one cycle

[‡]For up to two cycles

CONFIDENTIAL

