6.4.5 End of Treatment/Early Termination Visit

Patients will complete the study at the time of PD, if they withdraw consent, if they withdraw due to an AE, or at the time the study is terminated. If either study treatment or patients are discontinued, the reason will be recorded in the eCRF and source document. Patients who are removed from treatment for reasons other than death or disease progression (PD) are considered to be patients who have terminated early. Reasons for discontinuation include one of the following: AEs, protocol violation, patient withdraws consent, patient is lost to follow-up, administrative reasons (including study closure), death, or other. Patients who complete or discontinue from the study should have the following study completion/early withdrawal evaluations performed as soon as possible after the day of study completion/early withdrawal.

- Physical examination and vital signs

CONFIDENTIAL

STUDY DRUG: QUIZARTINIB
 PROTOCOL DATE: 10 AUGUST 2020

DEVELOPMENT INNOVATIONS STUDY NUMBER: AML 48
 VERSION 4.0

- ECOG performance status
- AE monitoring
- Concomitant medication review
- CBC and clinical chemistry panels
- BM biopsy and aspirate with FLT3 mutation testing, if applicable
- ECG and QTcF assessment, if applicable

Patients prematurely discontinuing from the study must be followed for AE and concomitant medication use for 30 days following the last administration of study drugs or until resolution/stabilization of an ongoing AE attributed to the medication.

Patients who discontinue from the study may be treated with other therapies at the discretion of the Investigator.

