10.2 Sample Size Considerations

The null hypothesis that the ORR (defined as CR + CRi) is $\leq 27\%$ (Cortes et al 2019) will be tested against a one-sided exact alternative ORR of 50% at a target significance level of 0.05. A sample size of 30 evaluable patients achieves 80% power if the true ORR is $\geq 50\%$. The null

CONFIDENTIAL

STUDY DRUG: QUIZARTINIB
PROTOCOL DATE: 10 AUGUST 2020

DEVELOPMENT INNOVATIONS STUDY NUMBER: AML 48
VERSION 4.0

hypothesis will be rejected if 13 or more responses are observed in 30 evaluable patients. In order to allow for a non-evaluable rate of 10%, a total of 34 patients will be enrolled in the study.

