10.3 Analysis Population

The following analysis populations will be used:

- The Safety Analysis Set is defined as all patients who received at least one dose of CPX-351 or quizartinib.
- The Efficacy Analysis Set is defined as all patients who received at least one dose of CPX-351 or quizartinib, who have an adequate baseline disease assessment, and an adequate post-baseline assessment and who discontinued due to death or PD prior to their first assessment.

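### The primary ORR excludes dosed patients who leave without an adequate marrow for reasons other than death or PD, which can only raise the observed rate against the fixed 27% null

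*Combined protocol and SAP*

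**What the plan says.** Section 10.4.2 defines ORR as the proportion with CR or CRi at the recovery assessment and adds "All efficacy analyses will be performed using the Efficacy Analysis Set". Section 10.3 admits to that set patients who had at least one dose, an adequate baseline disease assessment, and "an adequate post-baseline assessment and who discontinued due to death or PD prior to their first assessment". The all-dosed Safety Analysis Set is defined alongside it, but Section 10.4.3 uses it only for safety.

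Section 10.2 sets the test: a null ORR of 27% or less, which "will be tested against a one-sided exact alternative ORR of 50% at a target significance level of 0.05". It says "A sample size of 30 evaluable patients achieves 80% power", rejects at 13 or more responses in 30, and then: "In order to allow for a non-evaluable rate of 10%, a total of 34 patients will be enrolled in the study". No cutoff is given for any other evaluable number.

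No passage says how a dosed patient without an adequate marrow counts towards ORR. Section 9.4 defines treatment failure only at a response assessment. Section 9.7 has an EFS censoring rule for patients with no disease response assessment, so the plan accepts that such patients may exist.

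**The concern.** Taken literally, Section 10.3 requires both an adequate post-baseline assessment and discontinuation before the first assessment. Nobody could meet both, so the *and* before the death-or-PD clause must be meant as *or*. The point rests on that repair.

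Once repaired, the set names two kinds of early failure to keep: death and PD. Section 6.4.5 lists other ways of leaving: "Reasons for discontinuation include one of the following: AEs, protocol violation, patient withdraws consent, patient is lost to follow-up". A dosed patient who leaves by one of those routes before an adequate marrow is absent from both numerator and denominator. The numerator loses nothing, because no remission was documented, and the denominator shrinks.

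ORR is the only endpoint with a hypothesis test, and there is no control arm in which the same exclusions would partly cancel. Stopping for toxicity is an unsuccessful outcome of the regimen, and tolerability is the other primary objective. Yet such a stop improves the efficacy estimate, and near the cutoff it can decide the test.

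**Working it through.** **Inputs.** From Section 10.2: null 0.27, alternative 0.50, one-sided exact binomial, target alpha 0.05, 30 evaluable, cutoff 13, 10% non-evaluable, 34 enrolled. Exit rates other than 10% are assumptions used to show a range.

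**1. The plan's own design.** With X ~ Bin(30, p):
- P(X ≥ 13 | 0.27) = 0.0395, and P(X ≥ 12 | 0.27) = 0.0845, so 13 is the smallest valid cutoff.
- P(X ≥ 13 | 0.50) = 0.819.
- 30 / 0.90 = 33.3, rounded up to 34.

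The stated design reproduces.

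**2. Worst case at the boundary.** Assume all 34 are dosed and the 4 non-evaluable are non-responders.

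| Responders | Evaluable set (n = 30) | All dosed (n = 34) |
|---|---|---|
| 13 | 43.3%, p = 0.039, reject | 38.2%, p = 0.102, do not reject |
| 14 | 46.7%, p = 0.016, reject | 41.2%, p = 0.052, do not reject |
| 15 | 50.0%, reject | 44.1%, p = 0.024, reject |

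The exact cutoff is 15 at n = 34, against 13 at n = 30. With four exclusions, only 13 or 14 responders give different decisions.

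**3. Type I error against an all-dosed ORR of 27%.** Let each of 34 dosed patients independently have probability d of being an excluded non-responder. The evaluable number is then M ~ Bin(34, 1 − d), and the response rate among evaluable patients is 0.27/(1 − d). Take r(m) as the smallest cutoff with P(X ≥ r | m, 0.27) ≤ 0.05. The error is the sum over m of P(M = m) × P(X ≥ r(m) | m, 0.27/(1 − d)).

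| d (assumed) | ORR among evaluable | Type I error |
|---|---|---|
| 5% | 28.4% | 0.048 |
| 10% | 30.0% | 0.069 |
| 15% | 31.8% | 0.098 |

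Holding n at 30 with the 13 cutoff gives higher values (0.058 at 5%, 0.084 at 10%). The table is the fairer model, because the evaluable number will vary.

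**4. The all-dosed rule.** The exact cutoff is 13 for n = 28 to 30, 14 for n = 31 to 33, and 15 for n = 34. At n = 34, alpha is 0.024 and power at a true ORR of 50% is 0.804. If 50% holds only among evaluable patients and 10% exit, the all-dosed rate is 0.50 × 0.90 = 45%, and P(X ≥ 15 | 34, 0.45) = 0.606.

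**The case against.** An evaluable-patient denominator is common in phase II. The plan discloses it and sizes the trial on it. The test is defined on evaluable patients, so the inflation above exists only when 27% is read as an all-treated rate; the documents do not give that benchmark's denominator. This stands, and it is why the result is described as error against an all-dosed null.

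The exit route is also narrow. Early deaths and PD stay in. Induction starts as an inpatient, the first marrow is due at Day 21 (±2 days), and Section 6.4.5 provides an end-of-treatment marrow where applicable. Under Section 8.3.1 a severe toxicity does not by itself take a patient off study. Actual exclusions may therefore be few, and at 5% the error stays within 0.05. This limits the size but not the direction.

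A reader might infer four stronger things that the documents do not support:
- **That the 10% forecasts toxicity exits.** It inflates enrolment. Registration precedes treatment, and the set also requires a dose and an adequate baseline, so the four may include patients never dosed or without a baseline.
- **That Section 6.4.5 expects these exits before the first marrow.** Its list covers the whole study, including up to 24 maintenance cycles.
- **That "All patients will be assessed for response" in Section 5 promises an all-patient denominator.** It concerns assessment, not the denominator of the rate.
- **That more toxicity always means a better ORR.** Toxic deaths remain as failures.

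The strongest practical objection is power. If 50% was meant for evaluable patients, as Section 10.2's wording suggests, the all-dosed test falls from 0.82 to about 0.61. That is a real cost.

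**Conclusion.** The concern holds, with a certain direction and an uncertain size. On the *or* reading, the plan removes dosed patients without a documented remission from the only tested efficacy endpoint, and nothing else in the documents puts them back. The effect ranges from none, if every dosed patient has an adequate marrow, dies or progresses, to a reversed decision at 13 or 14 responders if all four allowed non-evaluable patients are treated non-responders. At an exit rate of 10% among dosed patients, type I error against an all-dosed 27% is about 6.9%. These figures assume that excluded patients count as non-responders, that exits are independent between patients, and that the cutoff is re-derived for the evaluable number. The documents do not support a claim that the ORR will be inflated by any particular amount.

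**What to change.** 1. **Section 10.3:** change the *and* before the death-or-PD clause to *or*.
2. **Sections 10.3 and 10.4.2:** compute the primary ORR and its exact test on all patients who received at least one dose. Count any dosed patient without a documented CR or CRi at the recovery assessment as a non-responder, whatever the reason. Keep the evaluable-set ORR as supportive.
3. **Section 10.2:** state the cutoff for the number actually treated (13 for 28 to 30, 14 for 31 to 33, 15 for 34). Say whether 50% refers to all dosed or only evaluable patients, and give the power for each: 0.80 and about 0.61 at n = 34.

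**Cost.** This changes wording only and adds no procedures. No patients are added if 50% is the all-dosed target. If it is an evaluable-only target (45% all-dosed), the sponsor either accepts power of about 0.61 or enrols more. The smallest n reaching 80% is 46 treated, with a cutoff of 18: P(X ≥ 18 | 46, 0.27) = 0.049 and P(X ≥ 18 | 46, 0.45) = 0.83.

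**Minimum alternative.** If the sponsor keeps the evaluable set as primary because of that power cost, it should retain dosed patients who stop for toxicity in the set as non-responders, and report the all-dosed ORR with its exact test beside the primary result.

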10.4.3 Safety Analysis

Safety will be assessed through the analysis of the reported incidence of treatment-emergent AEs. Treatment-emergent AEs are those with an onset on or after the initiation of therapy, and will be graded according to NCI CTCAE Version 5.0. A copy of the CTCAE scoring system may be downloaded from:

https://ctep.cancer.gov/protocolDevelopment/electronic_applications/docs/CTCAE_v5_Quick_Reference_8.5x11.pdf.

CONFIDENTIAL

STUDY DRUG: QUIZARTINIB
PROTOCOL DATE: 10 AUGUST 2020

DEVELOPMENT INNOVATIONS STUDY NUMBER: AML 48
VERSION 4.0

The AEs will be coded using the Medical Dictionary for Regulatory Activities (MedDRA) and summarized using system organ class and preferred term for all patients in the Safety Analysis Set. In addition, summaries of SAEs, AEs leading to treatment discontinuation, AEs by maximum NCI CTCAE grade, and AEs related to study treatment will also be presented.

Other safety endpoints including laboratory results, vital signs, ECG findings, and other protocol-specified tests will be listed and/or summarized for all patients in the Safety Analysis Set.

Concomitant medications will be coded using the WHO-Drug Dictionary, and they will be listed and summarized.

10.5 Analysis Time Points

10.5.1 Safety Review

The safety lead-in consists of the first 10 patients enrolled. If >3 patients experience delayed neutrophil count recovery >56 days from the first day receiving the study regimen, defined as having a peripheral blood ANC <500/ μ L without evidence of residual disease by BM biopsy, or if >3 patients develop a non-hematologic toxicity, defined as a Grade 4 non-hematologic AE determined to be probably related to the combined treatment, then the study will be terminated.

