4. PATIENT REGISTRATION

The patient must willingly consent to participate after being informed of the procedures to be followed, the experimental nature of the treatment, potential benefits, treatment alternatives, side-effects, risks, and discomforts. Institutional Review Board (IRB) approvals of this protocol and consent form are required. Eligible patients who wish to participate in the study will be enrolled into the study.

Registration must occur prior to the initiation of protocol therapy. Patients eligible to participate in the study may be enrolled by each site following the patient registration instructions provided by the Sarah Cannon Development Innovations (Development Innovations) study contact. Patient registration follow-up and/or confirmation will be provided via email within approximately 24 hours or by the next business day.

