6.4.1 Induction Phase

- Serum pregnancy test once per cycle during the induction phase

6.4.1.1 Cycle 1, Days 1, 3 and 5

- Physical examination and vital signs (Days 3 and 5)
- ECOG performance status (Days 3 and 5)
- AE monitoring
- Concomitant medication review
- CBC and clinical chemistry panel
- CPX-351 administration (Days 1, 3, and 5)

6.4.1.2 Cycle 1, Day 8

- Physical examination and vital signs
- ECOG performance status
- AE monitoring
- Concomitant medication review
- CBC and clinical chemistry panel

CONFIDENTIAL

STUDY DRUG: QUIZARTINIB
PROTOCOL DATE: 10 AUGUST 2020

DEVELOPMENT INNOVATIONS STUDY NUMBER: AML 48
VERSION 4.0

- ECG and QTc assessment
- Quizartinib daily on Days 8-21 (if QTcF \leq 450 msec)

6.4.1.3 **Cycle 1 Day 14**

- Physical examination and vital signs
- ECOG performance status
- AE monitoring
- Concomitant medication review
- CBC and clinical chemistry panel
- ECG and QTc assessment (if QTcF >470 msec, see Appendix F)

6.4.1.4 **Cycle 1 Day 21 (Response assessment)**

- Physical examination and vital signs
- ECOG performance status
- AE monitoring
- Concomitant medication review
- CBC and clinical chemistry panel
- BM biopsy and aspirate with FLT3 mutation testing via PCR
- ECG

6.4.1.5 **Cycle 1 Day 35 (\pm 7 days) (BM recovery)**

- Physical examination and vital signs
- ECOG performance status
- AE monitoring
- Concomitant medication review
- CBC and clinical chemistry panel
- BM biopsy and aspirate for MRD assessment via next-generation sequencing (NGS) and FLT3 mutation testing via PCR

6.4.1.6 **Cycle 2, Days 1 and 3 (re-induction, only applicable if patient achieves PR with recovery bone marrow after Cycle 1)**

- Physical examination and vital signs (Days 3 and 5)
- ECOG performance status (Days 3 and 5)
- AE monitoring
- Concomitant medication review
- CBC and clinical chemistry panels

CONFIDENTIAL

- CPX-351 administration (Days 1 and 3)

6.4.1.7 Cycle 2, Day 6

- Physical examination and vital signs
- ECOG performance status
- AE monitoring
- Concomitant medication review
- CBC and clinical chemistry panels
- ECG and QTcF assessment (if QTcF \leq 470 msec, resume quizartinib)
- Quizartinib (daily on Days 6-21, if QTcF \leq 470 msec)

6.4.1.8 Cycle 2 Day 14

- Physical examination and vital signs
- ECOG performance status
- AE monitoring
- Concomitant medication review
- CBC and clinical chemistry panel
- ECG and QTc assessment (if QTcF $>$ 470 msec, see Appendix F)

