10. STATISTICAL CONSIDERATIONS

10.1 Statistical Design

This is a multi-center, open-label, two-part prospective Phase II study of patients with relapsed or refractory FLT3-ITD mutation-positive AML. The study is designed to assess the safety and tolerability as well as the efficacy of administering CPX-351 with quizartinib, a second-generation FLT3 inhibitor.

A response rate (CR + CRi) of $\geq 50\%$ is targeted with 40% or less considered unacceptable. This is assumed to be an acceptable estimate based on CR + CRi/CRp of 48.2% reported with quizartinib monotherapy in a relapsed or refractory patient with FLT3-ITD AML (Cortes et al 2019). Of note, prior FLT3-targeting inhibitor exposure is permitted on this study. However, patients receiving a prior FLT3-targeting inhibitor were excluded in the QUANTUM-R study. Expected CR+CRi in relapsed or refractory patients receiving standard intensive or non-intensive salvage chemotherapy harboring an FLT3 mutation is 27% (Cortes et al 2019). The estimated response in those with relapsed/refractory FLT3-ITD AML receiving CPX-351 alone cannot be estimated. However, in a poor-risk EPI patient population, CR+CRi was reported as 39.3% (Cortes et al 2015). However, FLT3-ITD mutation presence was not utilized in the generation of EPI prognostication, and those with an FLT3-ITD mutation could in fact have a reduced response within all EPI risk groups. Thus, the expected response must be based upon the QUANTUM-R study of those receiving standard salvage options harboring an FLT3-ITD mutation.

In the safety lead-in, 10 patients will be enrolled to receive CPX-351 with quizartinib. If > 3 patients experience delayed neutrophil count recovery > 56 days or delayed thrombocytopenia recovery > 56 days from the first day on the study regimen, or if > 3 patients develop a non-hematologic toxicity, defined as a Grade 4 non-hematologic AE determined to be probably related to the combined treatment or a Grade 4 neutropenia, then the study will be terminated.

Assuming safety parameters are met, the first 10 patients will be followed for response in Part 2 of the study.

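### The safety lead-in is read on the first 10 patients enrolled, with no evaluability or replacement rule, so under the more-than-3-events wordings it can be passed because patients could not show an event

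*Combined protocol and SAP*

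**What the plan says.** Section 10.5.1 fixes the denominator by enrolment: "The safety lead-in consists of the first 10 patients enrolled". Section 10.1 agrees: "In the safety lead-in, 10 patients will be enrolled to receive CPX-351 with quizartinib". Enrolment comes before exposure, because Section 4 says "Registration must occur prior to the initiation of protocol therapy". Quizartinib starts a week after CPX-351 and depends on an ECG. In Section 6.4.1.2 the entry "Quizartinib daily on Days 8-21 (if QTcF" is followed by a limit of 450 msec.

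The stopping rule itself appears in several forms:

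- **Section 10.5.1:** "If >3 patients experience delayed neutrophil count recovery >56 days from the first day receiving the study regimen", where an event needs ANC below 500/μL "without evidence of residual disease by BM biopsy"; or more than 3 patients with a probably related Grade 4 non-hematologic event.
- **Section 5, Section 10.1 and Synopsis Statistical Methodology:** no marrow condition. They add platelets (in Section 5, "or delayed thrombocytopenia recovery >56 days from the first day on the study regimen") and a further item ("or a Grade 4 neutropenia, then the study will be terminated").
- **Synopsis Study Design row:** Part 2 opens if at least 8 patients meet the safety parameters.
- **Section 9.10:** defines delayed neutrophil recovery with no marrow condition.

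None of these says who is evaluable for the lead-in or whether anyone is replaced. The 10% non-evaluable allowance in Section 10.2 belongs to the efficacy test. Section 10.3 defines a dosed Safety Analysis Set, but the gate is not tied to it.

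**The concern.** Passing the gate allows 24 more patients to be treated. A rule that counts events among enrolled patients treats everyone without an event alike: those who tolerated the combination, those who did not receive it, and those who were gone before Day 56. The plan provides several routes to that last group. Patients may be registered and not dosed. They may fail the Day 8 QTcF check. Section 5 follows non-responders only until a new therapy starts, and Section 6.4.5 has patients complete the study at progression. The long-term follow-up in Section 6.4.6 lists disease response and survival, not blood counts.

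Under 10.5.1 there is a further restriction: a patient with persistent leukemia cannot be a neutrophil event but still fills one of the 10 places. Section 1.5 names pancytopenia with possibly prolonged neutropenia as the most anticipated side effect, so this criterion matters.

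**Working it through.** **Plan's own figures.** The only stated operating characteristics are for efficacy (Section 10.2). Rejecting at 13 or more of 30 gives an exact one-sided alpha of 0.0395 at 27% and power of 0.819 at 50%; 30/0.9 = 33.3, rounded up to 34. These reproduce. Nothing is stated for the lead-in gate.

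**Inputs.**
- Stopping count: more than 3, so at least 4 (all wordings except the Synopsis Study Design row).
- c, the chance of a disease-free marrow: not given. Proxies from Section 10.1 are CR+CRi of 27% (salvage), 39.3% (CPX-351, poor-risk) and 48.2% (quizartinib alone), plus the 50% target.
- t, the rate of non-recovery beyond Day 56: not given, so assumed over a range. The nearest documented rate is 17% beyond Day 42 with CPX-351 (Section 7.5.2).
- n, the number of the 10 able to show an event: assumed 10, 8 or 7.

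**Step 1: loss alone, no marrow condition.** P(stop) = P(X ≥ 4), X ~ Binomial(n, t), with lost patients contributing no event. At t = 50%:
- n = 10: 1 − (1+10+45+120)/1024 = 0.828
- n = 8: 1 − (1+8+28+56)/256 = 0.637
- n = 7: 1 − (1+7+21+35)/128 = 0.500

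At t = 30% the values are 0.350, 0.194 and 0.126.

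**Step 2: the 10.5.1 neutrophil criterion.** The per-patient event probability becomes q = c × t, with n = 10.

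| t | c = 27% | c = 39.3% | c = 48.2% | c = 50% | all 10 at risk |
|---|---|---|---|---|---|
| 30% | 0.006 | 0.023 | 0.044 | 0.050 | 0.350 |
| 50% | 0.035 | 0.115 | 0.203 | 0.224 | 0.828 |
| 80% | 0.151 | 0.389 | 0.581 | 0.618 | 0.999 |
| 100% | 0.273 | 0.600 | 0.797 | 0.828 | 1.000 |

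If c = 27%, fewer than 4 of 10 have a clear marrow with probability 1 − 0.273 = 0.727, and the criterion then cannot be met. With loss as well (n = 8, t = 50%), the four columns fall to 0.015, 0.053, 0.102 and 0.114.

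**Step 3: the other wordings.**
- Without the marrow condition, t = 50% and n = 10 give 0.828.
- If Grade 4 neutropenia is counted literally at an assumed rate of 80% to 95%, stopping has probability of at least 0.999.
- Under the Synopsis Study Design row, 3 or more failures block Part 2: 0.617 at 30% and 0.945 at 50%. If two untreated patients count as not meeting the parameters, one failure among the other 8 suffices: at 17%, 1 − 0.83⁸ = 0.77, against 0.234 with 10 at risk.

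**The case against.** A reader might infer that the gate as a whole can rarely stop a myelotoxic regimen. The documents do not support that. The marrow condition stands in 10.5.1 only. The Synopsis Statistical Methodology, Section 5 and Section 10.1 omit it and add platelet and Grade 4 neutropenia events, and the last of these, read literally, would stop the study almost always. Even within 10.5.1 the non-hematologic criterion can stop the study by itself: with c and t both 50% and an assumed independent 20% non-hematologic rate, the combined chance is 0.32 rather than 0.22. A reader might also infer that the denominator errs in the same direction in every wording. The at-least-8 rule may err the other way.

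The marrow condition is also a reasonable attribution rule, since neutropenia with persistent leukemia cannot be cleanly assigned to drug. Section 5.2 orders a marrow at Day 42 for this purpose. And c may exceed the response rate, because a disease-free aplastic marrow might qualify without being called CR or CRi. At c = 70% and t = 50% the criterion stops with probability 0.486.

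Nor is a patient stopped at the Day 8 check free of toxicity: three CPX-351 doses have been given, and the recovery clock runs from the first day of the regimen. For the non-hematologic criterion at an assumed 40% rate, P(stop) is 0.62 with 10 exposed and 0.41 if two patients contribute nothing, but 0.51 or 0.57 if those two carry a 20% or 30% rate. Repeat ECGs for up to 3 days (Section 6.5.3) limit such losses. Serious adverse event reporting and termination by the sponsor or IRB offer further protection.

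All of this stands and narrows the point. None of it supplies the missing evaluability rule.

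**Conclusion.** The concern holds in limited form. Under the more-than-3-events wordings, patients who could not show an event are counted as event-free, so the gate can be passed through non-evaluability. The loss effect is moderate: 0.83 to 0.64 or 0.50 at an assumed 50% event rate, if the lost patients contribute nothing. The marrow effect is larger but confined to the neutrophil criterion of 10.5.1: P(stop) is 0.04 to 0.22 at 50% non-recovery, 0.01 to 0.05 at 30% and 0.27 to 0.83 at 100%, for clearance of 27% to 50%. The comparison, if all 10 were at risk at 50%, is 0.83.

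The non-recovery rates and numbers lost are assumptions, and the response rates only stand in for marrow clearance. How much the marrow effect matters depends on which wording governs, which the documents leave open.

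**What to change.** Reconcile the Synopsis (both rows) and Sections 5, 9.10, 10.1 and 10.5.1 into one gate. Keep the sponsor's own count, but read it on 10 lead-in-evaluable patients:

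- **Non-hematologic criterion:** patients who received both drugs and either completed the observation period or had a qualifying event.
- **Count-recovery criterion:** patients followed past Day 56 or with an event. The sponsor should state whether the marrow condition applies and report how many patients were at risk. If the condition stays, the Step 2 figures remain low even with 10 followed, so that number is needed to interpret a pass.
- **Replacement:** draw replacements for non-evaluable patients from the 24 Part 2 places before Part 2 opens. With two replaced, 12 + 22 = 34.

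No new termination threshold is proposed. Apart from the wording changes, the gate may be read slightly later and the chance of stopping rises modestly. At a 17% event rate without the marrow condition, P(stop) goes from 0.033 with 8 at risk to 0.074 with 10.
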